10.5.3 Concomitant Medications and/or Other Treatments

GCs, which are required as part of the inclusion criteria, will be summarized by type of GC (prednisone vs. deflazacort), by schedule (daily vs. any other), and by dose level. Patients are required not to change the GC dose while on study. Any changes in doses or schedule will be listed.

Other concomitant medications will be summarized by ATC class and preferred term. Each medication will be counted once within a patient using it, regardless of the number of times it was reported on the eCRFs. The summaries will note new medications or supplements vs. those already given at baseline and study entry. Any other treatment, surgeries, will be listed and described; however, those are expected to be few without a need to be summarized using tables.

10.5.4 Cytokines, Antibodies and Pharmacokinetics

Cytokines and antibodies and pharmacokinetic concentrations will be summarized by dose level over time. Pharmacokinetic concentrations may be summarized at a later date. PK samples will only be analyzed in the event that anti-NS-065/NCNP-01 antibodies are detected in order to understand the impact of immunogenicity on plasma levels of the drug.

10.6 Efficacy Endpoints

All efficacy analyses will be performed using the FAS population. In addition, additional analyses will utilize historical control group data from the CINRG DNHS.

10.6.1 Primary Efficacy Objective

The primary efficacy outcome measure (TTSTAND) will be summarized by dose level over time using descriptive statistics. Actual values and change from the Pre-Infusion Visit (baseline from Study NS-065/NCNP-01-201) and change from Week 25 (baseline of the NS-065/NCNP-01-202 study) will be presented.

The TTSTAND times to perform the test will also be converted to velocities. (Note that a test result that is to be converted to velocity that the patient could not perform due to disease progression will have velocity set to zero only at the first visit where this occurs. After that visit, missing observations due to disease progression will be left as missing.). If needed, a data transformation or nonparametric approach will be performed for these assessments. Within patient changes and velocities (possibly transformed) will be tested using a one-sided paired t-test within dose level and within both dose groups combined.

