7.14.1. Time to Stand (TTSTAND) - Primary Efficacy Endpoint

TTSTAND will be performed by a CE at visits specified in the schedule of study assessments (Table 1). This test will assess the time it takes the patient to go from lying flat on the floor to standing and is administered as part of the NSAA (see Section 7.14.4). This test should take approximately 1 minute and is not associated with any risks. This test is routinely performed during standard clinical examinations of patients with DMD. The number of seconds required to perform the test and the 6-point rating scale of how the patient attains the standing position will be documented in source documents and captured in the relevant eCRF.

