7.14.3. Time to climb 4 stairs (TTCLIMB)

TTCLIMB will be performed by a CE at visits specified in the schedule of study assessments (Table 1). This test will assess the time it takes the patient to climb 4 stairs (23) including a 6-point rating scale to assess how the patient negotiates the stairs administered as part of the NSAA (see Section 7.14.4). This test should take approximately 1 minute and is not associated with any risks. The number of seconds required to perform the test will be documented in source documents and captured in the relevant eCRF.

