10.6.2 Secondary Efficacy Objectives

10.6.2.1 Analyses of NS-065/NCNP-01 patients only

TTRW, TTCLIMB, NSAA, 6MWT and QMT will be summarized by dose level over time using descriptive statistics. Actual values and change from the Pre-Infusion Visit (baseline from Study NS-065/NCNP-01-201) and change from Week 25 (baseline of the NS-065/NCNP-01-202 study) will be presented.

The TTRW and TTCLIMB times to perform the test will also be converted to velocities. For a test that the patient could not perform, the velocity will be set to zero. If needed, a data transformation or nonparametric approach will be performed for these assessments. Within patient changes and velocities (possibly transformed) will be tested using a one-sided paired t-test within dose group and within both dose groups combined.

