10.8 Handling of Missing Data

Every effort will be made to collect all data. However, despite best efforts, missing or incomplete data may be reported. All missing or partial data will be presented in the patient data listing, as they are recorded on the eCRF.

Patients lost to follow-up or withdrawn will be included in statistical analyses up to the point of their last evaluation. Unless otherwise specified, no imputation of values for missing data will be performed. Of note, since patients with DMD are expected to decline over time, imputing efficacy parameters by last value carried forward mostly biases towards patients appearing stronger or faster than they are, since it carries forward potentially a better value than the value at the time of the missed observation. Therefore, for this study, we will summarize how much data are missing, but do not expect to need to impute any data to accomplish the analyses as described. Details of handling missing data will be described in the Statistical Analysis Plan.

Missed assessments which occurred as a result of the COVID-19 pandemic will be entered on the COVID-19 Protocol Deviation Log by site personnel. It is anticipated that some or all assessments and laboratory tests required by the protocol schedule of events may be missed during the pandemic. Some of the missed assessments may be able to be collected at the next home or onsite visit. The missing data will be summarized in the Statistical Analysis Plan.

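### In the within-cohort analyses, the seconds summaries of TTSTAND, TTRW and TTCLIMB lose each boy once he can no longer do the test, and so understate decline

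*Combined protocol and SAP*

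**What the plan says.** **Recording.** Section 7.14.1 records for TTSTAND "The number of seconds required to perform the test and the 6-point rating scale of how the patient attains the standing position". Section 7.14.3 says for TTCLIMB "The number of seconds required to perform the test will be documented in source documents", and 7.14.2 does the same for TTRW. All three tests are therefore captured as times.

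**Within-cohort analysis.** Section 10.6.1 states "The primary efficacy outcome measure (TTSTAND) will be summarized by dose level over time using descriptive statistics", with actual values and changes from the Pre-Infusion Visit and from Week 25. It continues "The TTSTAND times to perform the test will also be converted to velocities". Section 10.6.2.1 has the parallel sentence for the other two tests: "The TTRW and TTCLIMB times to perform the test will also be converted to velocities". In both sections velocity is added to the summary of times and does not replace it. The synopsis describes the TTSTAND summary without mentioning velocity.

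**A boy who cannot do the test.** For TTSTAND, a boy unable because of disease progression "will have velocity set to zero only at the first visit where this occurs"; later visits stay missing. For TTRW and TTCLIMB, 10.6.2.1 sets velocity to zero with no limit to the first visit. Neither section gives a rule in seconds.

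**Testing.** Section 10.6.1 says "Within patient changes and velocities (possibly transformed) will be tested using a one-sided paired t-test within dose level", and also in the two dose groups combined. The unit of the changes is not stated.

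**Missing data.** Section 10.8 says "Unless otherwise specified, no imputation of values for missing data will be performed", promises a summary of how much is missing, and leaves details to the SAP.

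**Historical controls.** Section 10.6.2.2 compares the three timed tests as velocities, with zero when the test could not be performed.

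**The concern.** A time in seconds has no finite value for a boy who cannot complete the test; zero velocity does not convert back to a time. On the seconds scale he is therefore missing, and he is missing because he has declined most. The seconds mean and mean change then describe the boys still able, while a velocity mean with zeros describes everyone followed, so one endpoint is reported on two scales with two different sets of boys.

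This matters because follow-up is long. Boys entered Study 201 aged 4 to under 10 years and may be treated for 216 weeks in all, and 10.8 itself expects decline. That section rejects carrying the last value forward because it makes boys look stronger or faster than they are. It does not note that leaving out boys who have lost the test biases in the same direction. At stake are the descriptive TTSTAND tables for the primary efficacy measure and the matching TTRW and TTCLIMB tables. Section 10.1 plays down p-values, which leaves these descriptive means to carry more of the weight.

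**Working it through.** The plan states no sample-size calculation, effect size, SD or rate of loss for these tests, so there is no figure to reproduce. The check is the rules side by side, then the direction and possible size of the bias under stated assumptions.

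**1. Rules by scale**

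| Analysis | Scale | Value when the boy is unable |
|---|---|---|
| 10.6.1 TTSTAND | seconds | none |
| 10.6.1 TTSTAND | velocity | zero at the first such visit, then missing |
| 10.6.2.1 TTRW, TTCLIMB | seconds | none |
| 10.6.2.1 TTRW, TTCLIMB | velocity | zero |
| 10.6.2.2 versus controls | velocity | zero |

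Seconds are exposed throughout the within-cohort analyses. TTSTAND velocity is exposed too, after the first failed visit.

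**2. Direction: a worked example (times assumed)**

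Eight boys, baseline 3.0, 3.5, 4.0, 4.5, 5.0, 6.0, 7.0, 8.0 s; follow-up 3.5, 4.2, 5.0, 6.0, 7.5, 10.0, 14.0, 20.0 s. Every boy worsens. Now suppose the slowest 0, 1, 2 or 3 cannot do the test at follow-up. Velocity is 1/time.

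| Lost | Mean time (s) | Mean change (s) | Mean velocity change, zero kept (per s) | Mean velocity change, lost boys missing (per s) |
|---|---|---|---|---|
| 0 | 70.2/8 = 8.78 | 29.2/8 = +3.65 | −0.060 | −0.060 |
| 1 | 50.2/7 = 7.17 | 17.2/7 = +2.46 | −0.066 | −0.058 |
| 2 | 36.2/6 = 6.03 | 10.2/6 = +1.70 | −0.075 | −0.056 |
| 3 | 26.2/5 = 5.24 | 6.2/5 = +1.24 | −0.088 | −0.053 |

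As more boys lose the test, the mean change in seconds shrinks, while velocity with zeros shows more decline. The last column is what TTSTAND velocity does once the first-visit zero has passed: it shrinks as well.

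The paired t statistic need not follow the mean. For worsening in seconds it is 2.57, 2.77, 3.12 and 3.47 down the rows, because the boys removed also carried most of the variance.

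**3. Size: a simulation (all inputs assumed)**

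20,000 trials of 16 boys. Baseline velocity v0 has mean 0.25/s and SD 0.07, with all boys able at baseline. Annual velocity loss has mean 0.02, 0.03 or 0.04/s and SD 0.02. The period is 216/52 = 4.15 years, so v1 = v0 − loss × 4.15. A boy is unable if 1/v1 would exceed a limit of 10 or 20 s, or if v1 is not positive. The ratio is the able-only mean change divided by the mean change with unable boys scored at the limit.

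| Loss per year | Limit (s) | Unable | Able-only change (s) | Limit-scored change (s) | Ratio |
|---|---|---|---|---|---|
| 0.02 | 10 | 27% | 1.33 | 2.17 | 0.61 |
| 0.02 | 20 | 14% | 2.39 | 3.96 | 0.60 |
| 0.03 | 10 | 41% | 1.95 | 3.10 | 0.63 |
| 0.03 | 20 | 24% | 3.47 | 6.08 | 0.57 |
| 0.04 | 20 | 38% | 4.58 | 8.35 | 0.55 |

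The sixth combination (0.04, 10 s) leaves 56% unable and is left out because some simulated trials have too few able boys to summarise. Over 192 weeks, which matches change from Week 25, the five ratios are 0.59 to 0.67.

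In the five scenarios of the table the able-only mean change still showed worsening in at least 99.7% of trials, with a median t for worsening of 2.7 to 3.9.

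**4. A second model**

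Eight boys, log-normal baseline times (median 5 s, log-SD 0.4), mean log-increase 0.25, 0.5 or 0.8, lost above 15 s. On average 4% to 32% of boys were lost. In runs with at least one loss, the observed mean time was below the full-group mean every time. The observed mean change looked better in 98% to 100% of runs, by 0.8 to 4.9 s on average.

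**The case against.** **The comparison named in the efficacy objective is not on seconds.** That objective is TTSTAND against matched historical controls, and 10.6.2.2 runs it on velocity with zero. This stands, and it confines the point to the within-cohort analyses. A reader might infer that the historical-control result is biased in the same way; as written, it is not.

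**The paired test may not be in seconds.** The test sentence names no unit and closes the velocity paragraph, so it could mean changes in velocity. This stands as an ambiguity. The documents do not establish that seconds are tested, only that the sentence needs a unit.

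**The seconds results may not improve.** A reader might infer that boys dropping out makes the cohort appear to get better. Take 16 boys with mean 126/16 = 7.88 s; the two slowest (20 and 30 s) lose the test and nobody else changes. The mean falls to 76/14 = 5.43 s, 31% lower. But that compares unpaired means: each boy still measured has zero change between those visits. The simulated mean changes also still show worsening, and t can move either way. The supported claim is attenuation.

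**Other provisions may cover it.** Both sections allow a transformation or nonparametric approach if needed, 10.8 promises a summary of missing data, and its details go to a SAP that supersedes the protocol. None of these gives an unable boy a place on the seconds scale or separates inability from other missingness by visit. No separate SAP text is in the documents supplied, so a rule for seconds could exist there.

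**The magnitude is assumed.** This stands; no rate of loss, SD or time limit is in the documents.

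**Conclusion.** The concern holds for the within-cohort seconds summaries in 10.6.1 and 10.6.2.1. Followed as written, mean seconds and mean change in seconds at later visits rest on boys still able to do the test and understate decline whenever those lost are the ones who declined most.

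Under the assumed inputs, with 14% to 41% of boys unable after 216 weeks, the mean change is understated by 37% to 45% (1 − 0.63 to 1 − 0.55). Scoring unable boys at the limit is itself lenient, so within that model the understatement is a floor. It is not an estimate for this cohort: with few losses the bias is small, and with none it vanishes.

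The bias usually weakens the apparent decline without reversing it, and harm to the paired test's conclusion is not shown. Reconciling the velocity rules alone would not cure the seconds problem. Changing the scale alone would not cure TTSTAND, because its zero lasts for one visit only. The point merits a change before database lock; it does not undermine the study's main external comparison.

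**What to change.** In 10.6.1 and 10.6.2.1, and in the SAP and table shells:

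1. Make velocity the scale for means, mean changes and paired tests of the three timed tests, set to zero at every visit where the boy cannot do the test because of disease progression. In 10.6.1 this replaces the restriction to the first such visit.
2. State that the within-patient changes in the t-test sentence are changes in velocity.
3. Show seconds as medians and quartiles with unable boys ranked slowest. Alternatively, keep mean seconds but label it as boys able to do the test.
4. Print the numbers able and unable at each visit in the same table, with inability through progression separate from other missing assessments.

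No new measurement or change in clinical conduct is needed. The cost is SAP and table-shell wording and slightly more table work. The downside is that mean seconds, a familiar unit, becomes secondary.

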Test Product, Dose, and Mode of Administration	
NS-065/NCNP-01 Injection 250 mg aqueous infusions will be supplied as a 10-mL or 5-mL glass vial containing 25 mg/mL or 50 mg/mL of drug product in saline, respectively.
 
Patients will begin dosing in this study at the same dose level they received in Study NS-065/NCNP-01-201. Once sites receive IRB approval of Protocol Amendment 10, all subjects who were previously in the low dose cohort of 40mg/kg/week will receive 80mg/kg/week after obtaining patient consent/assent. Patients will continue at dose level of up to 80 mg/kg/week for the remaining duration of the trial, up to 192-week (up to a total of 216 weeks of treatment in Study NS-065/NCNP-01-201 and 202) extension study or enrollment in a separate long-term follow up program of NS-065/NCNP-01, whichever is earlier.
 
Investigational product will be prepared in accordance with an Investigational Product Instruction Manual (IPIM) and administered by intravenous infusion over a 1-hour period.

Safety Assessments	
 1. Overall incidence of adverse events (AEs) and serious adverse events (SAEs) 2. Changes from baseline compared to Screening Visit and Week 25 of Study NS-065/NCNP-01-201 in laboratory parameters (blood, urine). 3. Changes from baseline compared to Day 1 and Week 25 of Study NS-065/NCNP-01-201 in electrocardiograms (ECGs), anthropometrics, vital signs, and diagnostic parameters (physical exam). 4. Anti-NS-065/NCNP-01 antibodies at Weeks 37, 49, 73, 97, 121, 145, 169, 193 and 217 compared to Day 1 and Week 24 of Study NS-065/NCNP-01-201. 5. Anti-dystrophin antibodies at Weeks 37, 49, 73, 97, 121, 145, 169, 193 and 217 compared to Day 1 and Week 24 of Study NS-065/NCNP-01-201. 6. Cytokine levels at Weeks 37, 49, 73, and 97 compared to Day 1 and Week 24 of Study NS-065/NCNP-01-201.
Efficacy Assessments	
Primary:
 
Time to Stand (TTSTAND) at 37, 49, 61, 73, 85, 97, 109, 121, 133, 145, 157, 169, 181, 193, 205 and 217 Weeks compared to Pre-Infusion Visit and Week 25 of Study NS-065/NCNP-01-201.
 
Secondary:

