1.3.5.2. Phase II Trials

NS065/NCNP01-P1/2 is a Phase I/II study of NS-065/NCNP-01 Injection being conducted in Japan. This is a multicenter, parallel-group, open-label, 24-week study. Participants receive weekly IV administration of NS-065/NCNP-01 Injection 250 mg (40 mg/kg and 80 mg/kg) over 24 weeks. The primary efficacy endpoint of this study is dystrophin protein expression as measured by Western blot, immunofluorescence staining, and RT-PCR. 16 DMD patients amenable to Exon 53 skipping, aged 5-<18 years are enrolled.

NS-065/NCNP-01-201 is a Phase II study conducted in the United States and Canada. This is a multicenter, 24-week dose finding study to assess the safety, tolerability, pharmacokinetics and pharmacodynamics of NS-065/NCNP-01 in boys with DMD. Participants receive weekly IV administration of NS-065/NCNP-01 Injection 250mg (40 mg/kg and 80 mg/kg) or Placebo for the first 4 weeks, followed by weekly IV administration of NS-065/NCNP-01 Injection 250mg (40 mg/kg and 80 mg/kg) over the remaining 20 weeks. The primary efficacy endpoint of this study is dystrophin protein expression as measured by Western blot. 16 DMD patients amenable to Exon 53 skipping, aged 4-<10 years were enrolled.

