7.14.7. Ulnar Length

Ulnar length will be measured by a CE at visits specified in the schedule of study assessments (Table 1). In the event that a patient becomes non-ambulant the ulnar length will be utilized to impute height.

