10.6.2.2 Analyses comparing NS-065/NCNP-01 patients to historical controls

A matched data set from the CINRG DNHS data will be created. The purpose of the matching is to create a group data set that corresponds in characteristics to the patients in this study. The CINRG DNHS data set includes patients from age 2 years to over 30 years old, and some have been followed for close to a decade. Therefore, it is important to create a comparator group which will allow valid group comparisons. No patient to patient matched analysis is proposed. The sole purpose of the matching is to create a historical control group which is comparable in its basic characteristics to the study patient group. The final CINRG DNHS data set is expected to have between 16 and 32 patients included with time intervals of evaluations between 6 and 15 months. TTSTAND, TTRW, TTCLIMB, NSAA, 6MWT, and QMT results will be compared between the NS-065/NCNP-01 patients and the CINRG DNHS patients possibly using mixed-effects linear

models. The TTSTAND, TTRW, and TTCLIMB times to perform the test will be converted to velocities. For a test that the patient could not perform, the velocity will be set to zero.

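### TTSTAND velocity has two scoring rules once a boy can no longer stand, and the one in 10.6.1 drops him from later means and paired tests

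*Combined protocol and SAP*

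**What the plan says.** Section 10.6.1 (treated boys only) converts TTSTAND times to velocities. A test that the boy "could not perform due to disease progression will have velocity set to zero only at the first visit where this occurs". It continues: "After that visit, missing observations due to disease progression will be left as missing". Changes are then tested with one-sided paired t-tests, by dose level and pooled.

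Section 10.6.2.2 (comparison with CINRG DNHS controls) covers the same variable: "The TTSTAND, TTRW, and TTCLIMB times to perform the test will be converted to velocities". Its rule is: "For a test that the patient could not perform, the velocity will be set to zero". It has no first-visit limit and does not require that progression be the cause.

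Section 10.6.2.1 uses the unlimited zero rule for TTRW and TTCLIMB. That is an inconsistency between endpoints, not a contradiction about TTSTAND.

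Section 10.8 imputes nothing unless otherwise specified, so visits left missing by 10.6.1 stay missing. It rejects last value carried forward on the ground that "imputing efficacy parameters by last value carried forward mostly biases towards patients appearing stronger or faster than they are".

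**The concern.** The primary efficacy variable has two definitions, and the plan gives no reason for the difference. The same boy and visit could appear as zero in one table and be absent from another in the same report.

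The 10.6.1 rule also has a predictable bias. A boy who loses the ability to stand pulls the mean down once and then leaves it. Later means are taken over the remaining boys, who are the stronger ones, so a by-visit mean can rise while no boy improves. That is the same direction of error for which 10.8 rejects last value carried forward.

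Such losses are foreseeable. Section 1.3.5.2 describes the parent study: "16 DMD patients amenable to Exon 53 skipping, aged 4-<10 years were enrolled". Treatment runs for up to 216 weeks across the two studies, a little over four years. Section 7.14.7 provides for loss of ambulation: "In the event that a patient becomes non-ambulant the ulnar length will be utilized to impute height". The synopsis schedules 16 assessments: "Time to Stand (TTSTAND) at 37, 49, 61, 73, 85, 97, 109, 121, 133, 145, 157, 169, 181, 193, 205 and 217 Weeks". A boy who first fails at Week 121 scores zero once and is then absent from the 8 later visits, Weeks 133 to 217.

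**Working it through.** The plan states no figure that depends on this rule, so there is none to reproduce. The number of boys lost, the slopes and the threshold for loss below are all assumptions.

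**1. Closed form for mean velocity.** Let k of the n boys seen at a visit have failed at an earlier visit, with none newly unable, and let S be the summed velocity of the rest. The 10.6.1 mean is S/(n-k); with zeros kept it is S/n. The ratio is n/(n-k), an overstatement of k/(n-k).

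| n | k | Overstatement |
|---|---|---|
| 16 | 0 | 0% |
| 16 | 1 | 1/15 = 7% |
| 16 | 2 | 2/14 = 14% |
| 16 | 4 | 4/12 = 33% |
| 8 (one dose level, assumed half of 16) | 1 | 1/7 = 14% |
| 8 | 2 | 2/6 = 33% |

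**2. Worked example.** Eight boys have Week 25 velocities of 0.30, 0.28, 0.26, 0.24, 0.22, 0.20, 0.14 and 0.12/s (mean 0.220). The first six decline by 0.02/s per year and the last two by 0.03. A boy is unable below 0.05/s. Every boy declines at every visit.

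- Week 157 (132/52 = 2.54 years): the six sum to 1.195, the seventh boy is at 0.064 and the eighth fails for the first time. Mean = (1.195 + 0.064 + 0)/8 = 0.157 under both rules.
- Week 169: the six sum to 1.168 and the seventh is at 0.057. Under 10.6.1, 1.225/7 = 0.175; with zeros kept, 1.225/8 = 0.153.

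| Week | 10.6.1 mean (/s) | Zeros kept (/s) |
|---|---|---|
| 157 | 0.157 | 0.157 |
| 169 | 0.175 | 0.153 |
| 193 | 0.159 | 0.139 |
| 205 | 0.181 | 0.136 |
| 217 | 0.176 | 0.132 |

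The 10.6.1 mean rises twice; with zeros kept it falls throughout. At Week 217 mean velocity is overstated by 0.176/0.132 - 1 = 33%. Paired change from Week 25 is less affected: -0.074 against -0.088, so 0.014/0.088 = 16% of the decline is hidden.

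**3. Simulation.** 20,000 runs, no visit noise. Week 25 velocity has mean 0.22/s and SD 0.06, truncated at 0.08; loss is permanent below 0.05/s. Slope mean/SD is -0.01/0.02, -0.02/0.025 or -0.03/0.03 per second per year. The truncated version allows no boy to improve, which fits the expectation of decline in 10.8 better.

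| Result (16 boys unless stated) | Slope -0.01 | -0.02 | -0.03 |
|---|---|---|---|
| Decline hidden at Week 217, no boy improving | 10% | 17% | 22% |
| Decline hidden at Week 217, slopes untruncated | 21% | 28% | 34% |
| 10.6.1 mean rises at least once, no boy improving | 79% of runs | 97% | >99% |
| Same, 8 boys | 53% | 84% | 96% |

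With no boy improving and zeros kept, the mean never rises. With untruncated slopes, roughly 7%, 18% and 31% of boys are unable by Week 217; mean change reads -0.030, -0.052 and -0.066 under 10.6.1, against -0.037, -0.072 and -0.101 with zeros kept.

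**4. Control comparison.** This uses 16 treated boys, 32 controls, no drug effect and 8,000 runs. A two-sample t-test on change at Week 217 stands in for the possible mixed model. One rule in both groups gives 2.4% to 2.8% false positives in the drug's favour (nominal 2.5%). Scoring treated boys by 10.6.1 and controls by 10.6.2.2 would give 5%, 10% and 17%, but no section proposes this.

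**The case against.** The two rules sit in different analyses, and the note in 10.6.1 is worded for any test converted to velocity, so 10.6.2.1 and 10.6.2.2 could be read as shorthand for it. That reading does not help: it carries the loss of non-standing boys into more analyses.

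The protocol says in 10.1 that the SAP will supersede it, and in 10.8 that missing-data details will be in the SAP. This is fair, but no separate SAP text in the file settles the point.

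The primary objective is a comparison with matched controls, which is unaffected under one rule. Section 10.1 also plays down p-values. Under the simulation assumptions with 16 boys, a one-sided paired test for improvement at Week 217 was significant in under 0.1% of runs. With no boy improving, a test for decline was still significant in at least 99.9%. So the rule shrinks the displayed decline without creating a false claim of benefit. This stands and limits the impact.

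Losses would not be wholly hidden either: 10.8 promises a summary of missing data, and the NSAA scores rising from the floor. Part of each rebound is a single zero entering and then leaving the mean. Finally, stopping after the first zero is defensible for a linear mixed model, because repeated zeros flatten fitted slopes. None of this explains why by-visit means and paired changes should leave out boys known to be unable.

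**Conclusion.** The concern holds. Sections 10.6.1 and 10.6.2.2 give different rules for TTSTAND in current text, and the 10.6.1 rule biases treated-only by-visit means and paired changes towards better function. The wording difference and the direction of bias are certain. The size depends on how many boys lose the ability to stand: nil if none do, 7% to 33% on mean velocity for one to four earlier losses among 16, and 10% to 22% of mean decline hidden in the scenarios where no boy improves. The historical-control comparison is at risk only if the two groups are scored differently. This should be settled before database lock.

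**What to change.** State one TTSTAND velocity rule in 10.6.1 and 10.6.2.2, identical for study boys and DNHS controls: zero at every visit where the test cannot be done because ability has been lost, and missing only for other reasons such as COVID-19, injury, withdrawal or transfer to the long-term program. Print the number unable beside each by-visit mean. For by-visit tests, use the nonparametric option that 10.6.1 already allows. If a linear mixed model is used, give the first-zero-then-missing version as a sensitivity analysis in both groups.

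The cost is one or two sentences, a programming change and a recorded reason for each test not done. The downsides are more zeros, less normal data, less favourable means and flatter fitted slopes in boys who fail. In simulation with visit noise of 0.015/s (4,000 runs, least squares per boy), the median fitted slope of those boys was -0.044 to -0.054/s per year with zeros throughout, against -0.048 to -0.068 with one zero then missing.
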